## **3.0 Methods & Procedures**

### **3.1 Study procedures and assessments.**

- Screening and Enrollment: Prospective subjects will be considered for entry into the study. Subjects meeting the inclusion and exclusion criteria will be informed of the opportunity to participate in the study. Subjects will be entered into the study after providing written informed consent. Each subject will be instructed that if they decide not to participate, they may withdraw at any time.
- Randomization: Netarsudil ophthalmic solution 0.02% and placebo eye drops will be dispensed to study subjects in 2.5 ml bottles, identical in appearance. A designated, unmasked, dosing coordinator will apply a coded sticker to each bottle. A computer generated randomization table will be generated. After the study subject signs the informed consent document, the subject will be randomly assigned to receive netarsudil or placebo (netarsudil vehicle). Both the subject and the investigator will remain masked as to the assigned treatment. If a study participant elects to have both eyes enrolled in the study, the dosing coordinator will automatically assign the second eye to the opposite treatment group from that of the first eye.
- Study Treatment Regimen: Subjects will be instructed to instill the assigned eye drop into the study eye once nightly for the 3-month study duration or until 2 weeks after corneal clearing is complete, whichever occurs sooner.

- Study Drug Accountability: Subjects will be asked to bring back to the clinic all study bottles, both used and un-used. All study drug bottles will be reconciled and recorded.
- Rescue Medication: If corneal clearing is not complete or seems to have stalled at the 5-week exam, the investigator can ask the dosing study coordinator to reveal the randomization assignment. If the eye was randomized to placebo it can be treated once daily (at night) with netarsudil (open label) for 7 weeks, whereas if the eye was originally randomized to netarsudil, it can be treated twice daily with netarsudil (open label) for 7 weeks or until complete clearing, whichever is sooner, in lieu of using the masked study drop.
- Examinations:
  - Schedule: Study visits include screening, as well as 1 day, 1 week, 3 weeks, 5 weeks, 7 weeks, 9 weeks and 12 weeks after DSO (Table 1). If complete healing is noted at the 3-, 5- or 7-week exam, the next following exam can be omitted.

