  - Procedures: Medical and ophthalmic histories will be updated, adverse events will be recorded, and visual acuity will be assessed at each visit. A slit lamp examination will be performed at each visit to assess corneal clearing and to document any conjunctival or lid hyperemia, stromal inflammation, superficial punctate keratitis, other surface toxicity of the cornea, neovascularization of the cornea, and cells or flare in the anterior chamber. Subjects will also complete a 15-question visual disability questionnaire validated for use with FECD. Manifest refraction, intraocular pressure, ultrasonic pachymetry, and corneal imaging with anterior segment optical coherence tomography will be performed at selected exams as indicated in the Table. Corneal endothelial cell density will be measured by specular microscopy if possible at the 9- and 12-week exams. Any routine exam procedures that were already performed within 90 days of study enrollment do not have to be repeated at the screening exam.
  - Records release: Subjects may be asked to sign a records release form in case the subject sees another eye specialist while enrolled in the study.
  - Unscheduled examinations: Subjects will be instructed to return for extra examinations if they note any problems with the eye.
  - Study completion: Subjects will be considered to have completed the study after they complete the 12-week examination.

- Subject withdrawal or discontinuation: Each subject may voluntarily discontinue the study at any time they choose. Subjects who cannot complete the study for administrative reasons (e.g., non-compliance, failure to meet visit schedule, etc.) will be discontinued from the study. Discontinued subjects may be replaced. For subjects withdrawn from the study, the same measurements and assessments should be performed as done at the 3-month exit exam. Adverse events should be followed up until resolution or stabilization of the adverse event.

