#### **4.0 Risk/Benefit Assessment**

##### **4.1 Risks and Anticipated Adverse Events:**

Risks: This study is considered mild risk. It entails off-label use of netarsudil, which is approved for reduction of intraocular pressure in patients with open angle glaucoma or ocular hypertension.

A number of complaints and complications are anticipated in patients who have had DSO, regardless of whether they participate in this study. Therefore, the presence or absence of the following anticipated complaints and complications in the study eye will be recorded on the electronic case report form (eCRF) for each exam rather than on separate adverse event forms.

- Complaints of ocular discomfort: (examples include: eye pain, irritation, burning, itching, scratchy feeling, foreign body sensation, tired/fatigued feeling, achy/tender/sore feeling, pressure sensation, tightness, twinge/twitchy feeling, dry eyes, tearing/watering, eye redness) These are expected secondary to corneal decompensation with bullae in the area where Descemet's membrane has been removed and endothelial cells have not yet repopulated.
- Complaints of visual symptoms or disturbances: (examples include: glare or fluctuating vision, haloes around lights, diplopia, blurry, hazy, cloudy, filmy or out of focus vision,

ghosting or shadowing, difficulty reading, difficulty with night driving, floaters, spots in vision, light sensitivity, decreased vision, light reflections from intraocular lens or peripheral iridotomy). These are expected secondary to corneal decompensation with bullae in the area where Descemet's membrane has been removed and endothelial cells have not yet repopulated.

- Increased ptosis is expected secondary to corneal decompensation with bullae in the area where Descemet's membrane has been removed and endothelial cells have not yet repopulated.
- Puffy eyelids are expected secondary to corneal decompensation with bullae in the area where Descemet's membrane has been removed and endothelial cells have not yet repopulated.
- Delayed resolution of corneal haze or edema
- Subconjunctival hemorrhage
- Epithelial defect (within the first month of surgery) is expected secondary to corneal decompensation with bullae in the area where Descemet's membrane has been removed and endothelial cells have not yet repopulated.
- Development of capsular haze
- Superficial punctate keratitis

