Anticipated adverse events in subjects who had cataract surgery combined with DSO include cystoid macular edema and capsular haze. Cataract formation or progression is an anticipated adverse event in any eye that was phakic and underwent DSO without combined cataract surgery. These anticipated surgical adverse events will be recorded on the electronic case report form (eCRF) for each exam rather than on separate adverse event forms.

The most common anticipated adverse events associated with use of Rhopressa™ include: eye discomfort, irritation, itching or pain, foreign body sensation, increased tearing, blurry vision, conjunctival hyperemia, conjunctival hemorrhage, eyelid swelling, and verticillata. Additional adverse events reported with use of Rhopressa™ include: reduced visual acuity, allergic conjunctivitis, dry eye, keratitis, conjunctival swelling, photophobia, and corneal staining.

Adverse events: The type, severity, duration and frequency of the following anticipated adverse experiences and any other unanticipated ocular adverse events will be tabulated. If a patient experiences an adverse reaction, appropriate medical treatment will be provided. Examples may include:

- Intraocular pressure elevation which requires intervention
- Development of capsular haze which requires intervention
- Cystoid macular edema
- Iritis

Anticipated rare adverse events include retinal detachment, iris synechiae/atrophy, epiretinal membrane, infectious keratitis or conjunctivitis, branch retinal vein occlusion, or endophthalmitis.

Serious Adverse Event: A serious adverse event is one that results in any of the following outcomes: death, a life-threatening adverse event, inpatient hospitalization or prolongation of existing hospitalization, a persistent or significant disability/ incapacity, or a congenital anomaly/birth defect. In the event of a serious adverse event, the investigator will maintain complete documentation and promptly inform the study drug manufacturer and the governing Institutional Review Board (IRB) of the serious adverse event within their required reporting period.

Fellow eye: Patients in this population tend to be affected with the eye condition bilaterally, so many of the study subjects may undergo surgery on the fellow eye during study participation. Routine fellow-eye post-surgical complications will not be transcribed to the eCRF unless the fellow eye is enrolled in the study at the time of the event.

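### Only healed eyes may skip an exam, and at nominal times the skipped exam is the one at the last dose, so short-lived or symptom-free toxicity and IOP changes may be under-detected in early-clearing eyes

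*Combined protocol and SAP*

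**What the plan says.** Section 3.1 (Examinations) sets study visits at screening and at "1 day, 1 week, 3 weeks, 5 weeks, 7 weeks, 9 weeks and 12 weeks after DSO", which makes seven postoperative exams. It then adds: "If complete healing is noted at the 3-, 5- or 7-week exam, the next following exam can be omitted". The permission is optional and applies only to eyes judged healed. The text does not say whether it can be used more than once for the same eye.

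Under Study Treatment Regimen in the same section, the masked drop is used "once nightly for the 3-month study duration or until 2 weeks after corneal clearing is complete, whichever occurs sooner".

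Safety is ascertained at visits. Section 3.1 states: "Medical and ophthalmic histories will be updated, adverse events will be recorded, and visual acuity will be assessed at each visit". It continues: "A slit lamp examination will be performed at each visit to assess corneal clearing and to document any conjunctival or lid hyperemia", and goes on to list punctate keratitis and other surface toxicity. Table 1 places IOP at screening and at weeks 5, 7, 9 and 12, but not at week 3.

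Section 4.1 says that the listed post-surgical complaints and complications "will be recorded on the electronic case report form (eCRF) for each exam rather than on separate adverse event forms". On adverse events it says: "The type, severity, duration and frequency of the following anticipated adverse experiences and any other unanticipated ocular adverse events will be tabulated". No denominator is given, whether exams performed or time on drug.

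**The concern.** How often an eye is looked at depends on whether it has cleared, and faster clearing is what the drug is meant to produce (sections 1.1 and 3.2). If netarsudil works, more netarsudil eyes than placebo eyes will qualify to skip an exam. The skipped exam is also an informative one for drug safety, because it falls at the end of dosing.

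The adverse-event table by arm is at stake, and so is the interim adverse-event review by the safety committee every 6 months (section 4.2). Unequal ascertainment would tend to make netarsudil look better tolerated than it is, and the distortion would grow with efficacy.

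**Working it through.** **Inputs.** Visits, omission rule and dosing rule are from section 3.1; IOP visits and windows are from Table 1. Clearing is dated to the exam at which it is first noted, visits are at nominal times, and the slow eye has no rescue.

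**The plan's own count.** Day 1 and weeks 1, 3, 5, 7, 9 and 12 give 7 postoperative exams, in agreement with Table 1.

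**Applying both rules.** Last dose = week first seen clear + 2, capped at week 12. On-drug exams are those at or before the last dose.

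| First seen clear | Exams attended | Total | Last dose | On-drug exams (per week) | On-drug IOP readings |
|---|---|---|---|---|---|
| Week 3, rule used once | day 1; weeks 1, 3, 7, 9, 12 | 6 | week 5 | 3 (3/5 = 0.60) | 0 |
| Week 3, rule used twice | day 1; weeks 1, 3, 7, 12 | 5 | week 5 | 3 (3/5 = 0.60) | 0 |
| Week 5 | day 1; weeks 1, 3, 5, 9, 12 | 6 | week 7 | 4 (4/7 = 0.57) | 1 |
| Week 7 | day 1; weeks 1, 3, 5, 7, 12 | 6 | week 9 | 5 (5/9 = 0.56) | 2 |
| Week 9 | all | 7 | week 11 | 6 (6/11 = 0.55) | 3 |
| Never | all | 7 | week 12 | 7 (7/12 = 0.58) | 4 |

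For eyes clear at week 3, 5 or 7 the nominal last dose is at week 5, 7 or 9, and each of these is the visit that may be skipped. With nothing skipped, the week-3 eye would have 4 on-drug exams (4/5 = 0.80 per week), one of them at its last dose, and 1 on-drug IOP reading.

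**What the missing exam could hide (illustration).** Assume a sign that lasts d weeks, has its onset uniform over the dosing period, and can be seen only while present. An exam at week v catches onsets between v − d and v. The share detected is the length of dosing time so covered, divided by the dosing time.

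- d = 2, week-3 eye with week 5 skipped: onsets in weeks 0 to 3 are caught, 3/5 = 60%.
- d = 2, slow eye: all onsets are caught except those between weeks 9 and 10, 11/12 = 92%.
- d = 2, week-3 eye with week 5 kept: 5/5 = 100%.

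| Duration of sign | Week-3 eye, exam skipped | Week-3 eye, exam kept | Slow eye |
|---|---|---|---|
| 1 week | 40% | 60% | 50% |
| 2 weeks | 60% | 100% | 92% |
| 3 weeks | 80% | 100% | 100% |
| 4 weeks | 100% | 100% | 100% |

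The gap is confined to signs of short duration and closes when the exam is kept.

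**Between arms.** This needs the share of eyes clear at each visit, which the documents do not give. Assume shares clear at week 3/5/7/later of 10/20/20/50% on placebo, and either 30/30/20/20% or 50/30/10/10% on netarsudil, with the rule used twice where possible. Mean exams per eye are then:

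- Placebo: 0.1×5 + 0.4×6 + 0.5×7 = 6.4.
- Netarsudil: 0.3×5 + 0.5×6 + 0.2×7 = 5.9, or 0.5×5 + 0.4×6 + 0.1×7 = 5.6.

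**The case against.** A reader might infer that netarsudil toxicity is under-counted by design, and by a large amount. With an assumed independent 10% chance of an event per exam, 1 − 0.9^k is 41% for k = 5 and 52% for k = 7, a spread of 11 points with no true difference. The documents do not support that reading, for these reasons.

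- The spread compares two extreme eyes, not two arms. Under the assumed mixes above, the same formula gives 48.9% on placebo against 46.1% or 44.4% on netarsudil, a gap of 2.8 to 4.5 points. An arm gap of 11 points would need every netarsudil eye clear by week 3 and every placebo eye clear after week 7 or never.
- The formula counts exams after dosing has ended. For a week-3 eye, the week-9 exam comes 4 weeks after the last dose. At nominal times the rule removes one on-drug exam per healed eye, and on-drug exams per week are nearly equal (0.60 against 0.58). Fewer events from fewer weeks of drug is not under-counting. Independence between exams is also implausible for signs that persist.
- Omission is optional, and 5 exams requires using the rule twice, which the text neither grants nor forbids.
- Visit windows can restore an exam at the last dose. Clearing noted at week 4 means dosing to week 6, when the week-7 exam may fall.
- Histories are updated at every visit, subjects are told to come back for extra exams when they notice trouble, and the table is to include duration. Symptomatic or lasting events can therefore still be recorded. Section 4.1 plans tabulation and describes no formal between-arm safety test.

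All of this stands as a limit on size. It does not remove the point. A sign without symptoms prompts no extra visit. For complications recorded exam by exam, a skipped exam leaves no entry of its own. An IOP change between weeks 3 and 5 in an eye that skips week 5 has no scheduled reading to show it while on treatment.

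**Conclusion.** The point holds in a limited form. Ascertainment depends on an outcome that the drug is meant to change, and at nominal times the exam that may be lost is the one at the last dose. A week-3 eye can have 6 postoperative exams, or 5, against 7; it can go unexamined for 2 of its 5 dosing weeks and have 0 scheduled on-treatment IOP readings where keeping the exam would give 1.

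The plausible direction favours netarsudil, but what may be missed is mainly short-lived or symptom-free signs and IOP changes. The size cannot be computed, because the documents give neither rates of complete clearing by visit nor adverse-event rates; the detection percentages and clearing mixes above are illustrations under stated assumptions. The conclusion rests on nominal visit times, on the option being used, and on netarsudil eyes clearing sooner. It is worth correcting because the correction is cheap, not because a large bias has been shown.

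**What to change.** 1. In section 3.1, do not allow the first Table 1 exam after complete clearing is noted to be omitted, and record adverse events, IOP and bottle return there. Dosing rules are unchanged. State also whether any later exam may be omitted.
2. In section 4.1 or 3.2, tabulate adverse events by randomised arm over the exams that precede any omission or rescue (1 day, 1 week, 3 weeks) as the like-for-like comparison. Report later events per week on the assigned drop, with off-drug time and open-label netarsudil time shown separately.

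A week-12 comparison or a rate per exam performed would not serve. By week 12 early-clearing eyes have been off drug for weeks, while slow placebo eyes may have had open-label netarsudil after week 5. A per-exam denominator would also dilute drug effects with off-drug exams.

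Cost: healed eyes attend one exam that is already scheduled, and one more table is needed.

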### **2.0 Characteristics of the Research Population**

2.1 **Number of Subjects:** up to 60 FECD patients will be enrolled.

2.2 **Gender of Subjects:** both men and women will be enrolled

2.3 **Age of Subjects:** 18-90 years of age. The rationale for not including minors is that endothelial keratoplasty is performed to treat endothelial dysfunction, a condition usually seen in adults over 40 years of age.

2.4 **Racial and Ethnic Origin:** Subjects may be of any racial or ethnic origin.

2.5 **Inclusion criteria.** The following are requirements for study inclusion:

- At least 18 years of age
- Male or female patient undergoing Descemet stripping only for Fuchs dystrophy.
- Patient is able and willing to administer eye drops.
- Patient is able to comprehend and has signed the Informed Consent form.

**2.6: Exclusion criteria.** Patients with any of the following cannot participate in the study:

- Active intraocular inflammation, corneal ulceration, keratitis, or conjunctivitis.
- Known sensitivity to any of the ingredients in the study medications.
- Abnormal eyelid function.
- History of herpetic keratitis.
- History of non-compliance with using prescribed medication.
- Current or planned pregnancy within the study duration.
- Concurrent involvement or participation in another randomized clinical trial within 30 days prior to enrollment in this study.
- Any ocular or systemic condition (i.e., UNCONTROLLED systemic disease) or situation which in the investigator's opinion may put the patient at significant

risk, confound the study results, or interfere significantly with the patient's participation in the study.

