**Table 1.**

	Screening Randomization	1 day after DSO	7 ± 2 days after DSO	3 ± 1 weeks after DSO	5 ± 1 weeks after DSO	7 ± 1 weeks after DSO	9 ± 1 weeks after DSO	Exit visit 12 ± 2 wks after DSO
Informed Consent	X							
Inclusion/Exclusion Criteria	X							
Medical and ophthalmic history	X	X	X	X	X	X	X	X
Adverse Events	X	X	X	X	X	X	X	X
Uncorrected visual acuity (Snellen)	X	X	X	X	X	X	X	X
Visual disability questionnaire	X			X	X	X	X	X
Assignment to netarsudil or placebo	X							
Manifest refraction and corrected distance vision (Snellen) if possible	X			X	X	X	X	X
Slit lamp exam	X	X	X	X	X	X	X	X
Endothelial cell density (if possible)							X	X
Intraocular pressure	X				X	X	X	X
Ultrasonic pachymetry	X				X	X	X	X
Anterior segment optical coherence tomography	X			X	X	X	X	X

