### 3.2 Data Analysis and Data Monitoring:

The primary endpoint is the proportion of corneal clearing at 4 and 6 weeks after DSO. Based on previous pilot studies, we estimate that the mean proportion of corneal clearing in the placebo

arm will be 0.6 vs. 0.8 in the Rhopressa arm. The standard deviation is estimated to be  $\pm 0.30$ . A sample size of 29 per study arm (total = 58) would provide 80% power to detect a statistically significant difference between groups at a 5% significance level (one-sided test). The planned enrollment is 60 subjects; this anticipates 3% drop out prior to the 4-week primary endpoint.

Statistical analysis will be conducted on an intent-to-treat basis (i.e. all randomized subjects will be included in the analysis). Data will be analyzed with Statistical Analysis Software (SAS Version 9.4, SAS Institute, Cary, NC).

**3.3 Data Storage and Confidentiality:** Research data will be stored in a locked cabinet or locked room and on a password protected server to prevent unauthorized access to data. The investigators and research staff will have access to the data. Subject identifiers will be removed and data will be aggregated for publication or presentation of study results.

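### Subjects discontinued for non-compliance or missed visits before week 4 or 6 have no clearing value at the primary times, though all randomized subjects are to be analysed

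*Combined protocol and SAP*

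**What the plan says.** Section 3.1 (Subject withdrawal or discontinuation) states: "Subjects who cannot complete the study for administrative reasons (e.g., non-compliance, failure to meet visit schedule, etc.) will be discontinued from the study". It then allows substitution: "Discontinued subjects may be replaced". The remaining clinical data collection is one exam: "For subjects withdrawn from the study, the same measurements and assessments should be performed as done at the 3-month exit exam". Adverse events are followed to resolution or stabilization, but no later clearing assessment is requested.

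Section 3.2 states: "The primary endpoint is the proportion of corneal clearing at 4 and 6 weeks after DSO". The analysis is by intention to treat and includes every randomized subject. The plan is for 60 subjects, which allows for 3% dropout before the 4-week time. Section 2.1 limits enrolment: "up to 60 FECD patients will be enrolled". Section 3.1 (Randomization) lets a participant enrol both eyes, with the second eye assigned to the opposite arm.

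No section says how a missing primary value is handled or how a replaced subject enters the analysis.

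**The concern.** The discontinuation rule ends study participation, not only use of the drop. A subject who uses the drops poorly, or who has missed a visit, may still be able to attend a later slit-lamp exam, which the plan schedules at every visit. Once such a subject is discontinued before week 4 or week 6, the only further clearing value is dated at withdrawal. An analysis of all randomized subjects cannot recover a value that the protocol told the site not to collect.

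The loss need not be balanced. Section 4.1 lists eye discomfort, irritation and conjunctival hyperemia among the most common effects of Rhopressa, and these could lower compliance in that arm. The same section expects ocular discomfort after the surgery in either arm. The documents therefore give a reason to think the loss may depend on treatment, but do not show how much or in which direction.

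The 3% allowance covers loss before week 4 only. Loss between weeks 4 and 6 affects the second primary time and has no allowance.

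**Working it through.** **Inputs.** From section 3.2: mean clearing 0.6 on placebo and 0.8 on Rhopressa (difference 0.20), SD 0.30, one-sided 5% test, 29 per arm (58 in total) for 80% power, 60 enrolled with 3% dropout. The numbers of lost subjects below are assumptions. Each subject is treated as one independent eye.

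**The plan's own figure.** Two-sample t test, noncentrality = 0.20 / (0.30 × √(2/n)), with 2n − 2 degrees of freedom.
- n = 29: noncentrality 2.539, critical value 1.673, power 0.806.
- n = 28: power 0.793, below 0.80.

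So 29 per arm reproduces. Enrolment: 58 / 0.97 = 59.8, rounded up to 60, also reproduces. The planned loss is 0.03 × 60 = 1.8, about 2 subjects.

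**Power as values are lost.**

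| Observed per arm | Lost of 60 | Power |
|---|---|---|
| 30 / 30 | 0 | 0.818 |
| 29 / 29 | 2 (planned) | 0.806 |
| 28 / 28 | 4 | 0.793 |
| 27 / 27 | 6 | 0.780 |
| 28 / 30 | 2, all in one arm | 0.805 |
| 26 / 30 | 4, all in one arm | 0.792 |

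Power falls by about four percentage points between no loss and six losses (0.818 − 0.780 = 0.038).

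**Possible bias.** Clearing is a proportion between 0 and 1, so one unobserved value can move an arm mean of 30 by at most 1/30 = 0.033. Two in the same arm can move it by at most 2/30 = 0.067, which is 0.067 / 0.20 = one third of the planned difference. That is an extreme bound.

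A milder case, by assumption: a fraction f of an arm is lost, and those subjects lie g below the full-arm mean. The observed mean then rises by g × f / (1 − f). With f = 2/30, f / (1 − f) = 2/28 = 0.0714.
- g = 0.2: shift 0.014.
- g = 0.4: shift 0.029.

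If the lost subjects lie above the mean, the shift has the opposite sign.

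**Replacement against the counts.** If the planned 60 and the limit of 60 both count people with one eye each, the room for replacements is 60 − 60 = 0. If 29 per arm counts eyes, each participant with two enrolled eyes supplies one value to each arm, the target is met with fewer people, and there is room. The documents do not say which applies.

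**The case against.** The strongest case against is that the effect is small and the rule is narrower than it first appears. It covers subjects who cannot complete the study, and does not plainly say that every non-compliant subject who still attends is removed. Some subjects will be lost under any rule. Section 2.6 already excludes this group: "History of non-compliance with using prescribed medication". The figures above show little loss of power. All of this stands and limits the weight of the point. It does not remove it, because the sentence names non-compliance as a reason for discontinuation and no later clearing data are requested.

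A reader might infer stronger conclusions that the documents do not support:
- **That every discontinued subject loses primary data.** Only discontinuation before week 4 or week 6 does. The exit-type exam includes a slit-lamp exam, so a clearing value exists, and a withdrawal in weeks 4 to 6 falls within the "5 ± 1 weeks after DSO" window.
- **That replacement is impossible under the limit, or removes subjects from the analysis.** The first depends on whether the counts are of eyes or people. The second does not follow, since not counting someone toward enrolment differs from excluding them from the analysis, and section 3.2 includes all randomized subjects.
- **That the permitted visit omission is a comparable loss.** Section 3.1 says: "If complete healing is noted at the 3-, 5- or 7-week exam, the next following exam can be omitted". An eye healed at week 3 may miss week 5, but complete clearing is already documented and the 3- and 7-week visits bracket the gap. If such eyes are scored 1.0 and clearing persists, the primary contrast is unchanged.

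**Conclusion.** The point holds in a limited form. The discontinuation rule leaves the all-randomized analysis without 4- or 6-week clearing values for subjects removed earlier, and part of that loss is avoidable. Bias is possible because compliance follows randomization and may depend on treatment, but its size and direction are unknown and it is probably small. Power runs from 82% with 60 observed to 79% with 56 and 78% with 54. The bound for two losses in one arm is 0.067, and the assumed milder cases give 0.014 to 0.029.

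These figures rest on the plan's means and SD, on assumed numbers of losses, and on one independent eye per subject. A discontinued participant with both eyes enrolled could lose a value in each arm, which the table does not model. The stated sample size is not in dispute. The wording on replacement and the enrolment limit needs reconciling, but it is not shown to be a contradiction.

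**What to change.** 1. Amend section 3.1 so that non-compliance or a missed visit does not end data collection. Such subjects stay in the 3-, 5- and 7-week and exit visits already scheduled, unless they withdraw consent. This concerns data collection only, not whether the drop is continued.
2. State in section 3.2 that a replaced subject remains in the all-randomized analysis set. Reconcile the replacement sentence in section 3.1 with the limit in section 2.1 and the planned 60 in section 3.2, and say whether these numbers count eyes or people.
3. For primary values still missing, add a bounding analysis that sets them to 0 and to 1. If a repeated-measures model is used, it must account for open-label netarsudil, which section 3.1 allows after the 5-week exam, and for two eyes from one participant.

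The cost is protocol wording, a few scheduled visits that would otherwise not take place, and a little more analysis. These changes do not settle which visit supplies the 4- and 6-week values, since no visit is scheduled at either time; that must be stated separately.
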